3.0 STUDY DESIGN

This is a pilot, parallel randomized controlled trial of CGM versus a standard finger-prick protocol among patients with type I and II diabetes treated at Intermountain Healthcare’s Reimagine Primary Care Clinics. Patients will

be eligible if their most recent HbA1c level is $\geq 6.5\%$ and they are either currently using a glucose meter or are prescribed a glucose meter at their index encounter. Upon consent, which will occur within in a private office/room within the Reimagine Care Clinic, patients will be randomized into one of two groups:

- **Intervention group:** CGM using a Dexcom G6 to measure glycosylated hemoglobin levels every five minutes. Patients will be asked to download the Dexcom G6 and Clarity applications (to have access to their real-time data) and be given a link to complete an exit survey in REDCap near the end of their study participation. Data will be sent via Bluetooth and then exported by the Intermountain research team into a Tableau (or similar) dashboard for data analysis/comparison (**Appendix A**)
- **Control group:** A standard finger-prick protocol that will require patients to continue with their daily fingerprick regimen established by their physician. This group will be given a Contour Next One meter to ensure that each patient is receiving the same level of accuracy by the same device. A review by Ekhlaspour et al of 17 glucose meters demonstrated wide variability, with only two devices achieving the 2013 ISO standard (with the most accurate being the Contour Next) [7]. Patients in the control group will be asked to download the Contour Next application which will send data via Bluetooth similar to above. Data will be aggregated, and protected health information removed prior to analysis (by Intermountain Healthcare and Savvysherpa). At the end of the study, patients will be asked to complete a short survey in REDCap about their willingness to participate in future studies (**Appendix A**).

Randomization will be assigned *a priori* using a random number generator from Microsoft Excel. Sub-Investigator will then transcribe these numbers and order them individually in concealed envelopes and present them to the Research Coordinators to ensure the CRC is blinded. At time of consent the Research Coordinator will hand the patient the earliest numbered envelope to randomize. . Patients in both randomized groups will be given the devices and one month supplies to ensure compliance with the protocol. The Study Coordinator and patient will exchange contact information so that the CRC may resupply the patient with necessary equipment at the end of their month supply. The CRC may meet the patient at their Reimagine Care Clinic or off site for patient convenience. All patients are expected to participate for six months, which is near the minimum duration sufficient to measure clinically meaningful changes in hemoglobin A1c related to gradual behavioral changes (e.g., diet, exercise, insulin administration). Further, each patient will complete 2 mandatory blood draws and one elective blood draw at their designated Reimagine Care Clinic to evaluate HbA1c level changes over the course of the study. Baseline HbA1c must be completed on day of enrollment (± 2 days) which Intermountain Healthcare may choose to cover if not paid for by patient's SOC. An elective blood draw will be considered for data if completed at 3 months (± 1 week) and a third required blood draw upon study completion (± 2 weeks) which the study may also choose to cover if not SOC. 2 weeks from 180 enrollment) which the study may pay for if not covered by patient's SOC. We postulate that those that have a more consistent interstitial glucose profile (which avoid the high peak to valley swings), will have a more pronounced difference in pre and post HbA1c levels. Specific Aim #1 above will help our team understand the relationship between interstitial glucose and HbA1c, along with other outcomes of interest which include weight loss, alterations in diet, change in physical activity, etc.

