- **Hypothesis for Aim 3a:** Greater than 80% of patients who will have been approached to participate in this study will consent to participation.
- **Process for Aim 3a:** The team will record the number of patients approached, consented and those that participate in this study. Metrics will be helpful for estimating future recruitment in other Reimagine Primary Care studies.

Specific Aim 3b: Understand patient satisfaction with CGM

- **Hypothesis for Aim 3b:** Patient’s will be satisfied with CGM device.
- **Process for Aim 3b:** Develop and deploy exit surveys targeting patients randomized to CGM to assess satisfaction with the CGM device and related digital health monitoring services.

Specific Aim 3c: Understand how CGM changed patient behavior

Hypothesis for Aim 3c: Patients will have felt empowered by CGM.

- **Process for Aim 3c:** Within the survey developed/deployed per Aim 3b, include 5-point Likert-based questions soliciting patient opinions and perspectives. Summarize those perspectives so that research investigators and operational leaders can use this information to change clinical operations (as needed).

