3.3 Screening and Selection of Subjects

Subjects will be screened and recruited by Research Coordinators with CITI/HIPAA training. These coordinators will be trained in advance by Drs. [name] and [name], on how to instruct patients of proper usage of their device, how to effectively interact with subjects, the questions that may be posed, how patients should interpret feedback from the devices/cellphones, etc. [name] will also consult with the providers so that they understand the questions that may be asked by the patients and how to provide best care practices.

If a patient agrees to participate, a consent form will be electronically signed using REDCap. Participants will receive a paper copy of the consent containing all relevant and study pertaining information including important contact information. The subject will then be randomized into a study group and given the appropriate device by a Research Coordinator. Each patient will download the mobile apps relevant to their group, so their data can be tracked and transmitted by the study team.

- Group #1 will download the Dexcom G6 and Clarity apps
- Group #2 will download the Contour Next ONE Diabetes application.
- Both groups will also use REDCap to complete the end of study survey (**Appendix A**).

All devices will be registered prior to study startup and will be matched to a deidentified subject identifier (e.g. Subject_001). The coordinators will answer any study related questions that the patients may have before and during the study along with the Reimagine Primary Care clinicians who have agreed to participate as collaborators during the patient's regular appointments. Before patient's leave the clinic, (or ± 2 days) a blood draw will be conducted at the Reimagine site by a certified phlebotomist or approved healthcare provider to collect initial HbA1c level.

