5.0 END OF STUDY CONSIDERATIONS

5.1 Study Completion

A participating subject will be considered to have completed the study if and only if:

- He/she completed the treatment/intervention course described in this protocol
- He/she has complied with all the procedures and completed the two required blood draws within the allowable window
- He/she finished the exit survey

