5.2 Voluntary Withdrawal of Consent

Subjects shall have the ability to withdraw consent for study participation and/or the use of their clinical information at any time and for any reason, without penalty or loss of benefit to which the subject is otherwise entitled, by contacting the Principal Investigator or a designated member of his research team, preferably in writing and addressed to the Principal Investigator at the address indicated on the cover page of this protocol.

In the case a subject enrolled in this study decides to withdraw from the research, or an Investigator decides to terminate a subject's participation, study investigators must follow accepted standard practices regarding the management of collected data about these subjects, as follows:

- Investigators must document in the research record each instance of a subject withdrawal, including the reasons for the withdrawal, if known.
- If the subject withdraws and does not consent to continued follow-up and collection of clinical information, the investigator(s) will discontinue access to the subject's medical record or other confidential records, for purposes related to the study.
- Following the subject's withdrawal from the study, the Study Team will no longer contact the subject nor have access to his/her medical records for research purposes (unless specific informed consent has been obtained as described above).

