12.0 APPENDIX A

This section provides the questions which will be entered into REDCap and patients asked to complete at the end of the CGM study. There will be branching logic used based on the specific group assigned.

- 1. Which group were you assigned to?**
 - a. Group 1 (Dexcom G6)
 - b. Group 2 (ContourNext One)
- 2. What was the main reason that you signed up for this trial? _____.**
- 3. What was your biggest concern when you considered participating in this trial? _____.**
- 4. Were you initially disappointed with your group assignment?**
 - a. Yes
 - b. No

4b. Why were you disappointed with your group assignment? _____.
- 5. (For Group 1 participants): Did the Dexcom G6 impact your glucose management? For example, did it change your diet?**
 - a. Yes
 - b. No
- 6. (For Group 1 participants): Did the Dexcom G6 impact your glucose management? For example, did it change your exercise regimen?**
 - a. Yes
 - b. No
- 7. How did Dexcom G6 impact your glucose management? _____.**
- 8. (For Group 1 and 2 participants): On a scale of 1-5, where 1 is not helpful and 5 is extremely helpful, how would you rate the device?**
- 9. (For Group 1 and 2 participants): On a scale of 1-5, where 1 is extremely poor and 5 is extremely healthy, how would you rate your health BEFORE starting this study?**
- 10. (For Group 1 and 2 participants): On a scale of 1-5, where 1 is extremely poor and 5 was extremely healthy, how would you rate your health AFTER starting this study was completed?**
- 11. (For Group 2 participants): Did the ContourNext One impact your glucose management? For example, did it change your diet?**
- 12. (For Group 2 participants): Did the ContourNext One impact your glucose management? For example, did it change your exercise regimen?**
- 13. How did the ContourNext One impact your glucose management? _____.**
- 14. Did your glucose levels decrease between the initial enrollment and the end of the study? (Suggest inserting this filter question.)**
 - a. They increased
 - b. The decreased

c. No change

15. Would you be willing to participate in future Intermountain pilots in your primary care clinic? a.

Yes

b. No

16. General Comments. In the space provided, please feel free to add any other comments regarding your participation in this study. _____.

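### CGM patients who leave the study early have no planned exit survey, so Aims 3b and 3c would rest mainly on those still enrolled at six months

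*Combined protocol and SAP*

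**What the plan says.** **Target.** The process for Aim 3b (Section 2.0) is to "Develop and deploy exit surveys targeting patients randomized to CGM to assess satisfaction with the CGM device". Aim 3c uses Likert questions in the same survey. No other source is planned for either aim. The synopsis lists self-reported behavioral change and perceptions of the technology among the secondary endpoints.

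**Timing.** Three places set it:
- Section 3.0, CGM arm: patients will "be given a link to complete an exit survey in REDCap near the end of their study participation".
- Section 3.3: "Both groups will also use REDCap to complete the end of study survey".
- Appendix A: questions that will be entered into REDCap and "patients asked to complete at the end of the CGM study".

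**Leaving early.**
- Section 5.2 (withdrawal): afterwards "the Study Team will no longer contact the subject nor have access to his/her medical records for research purposes", with the exception "unless specific informed consent has been obtained as described above". Each withdrawal is documented, "including the reasons for the withdrawal, if known".
- Section 5.3: patients may be terminated after failed attempts to regain compliance.
- Section 5.4 (loss to follow-up): up to three calls or emails, then possibly a certified letter.
- None of the three sections mentions the survey.

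**Completion.** One of the conditions for study completion in Section 5.1 is "He/she finished the exit survey".

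**The concern.** The aim names everyone randomized to CGM, but the procedure reaches people who are still in the study when it ends. Patients who withdraw because of skin irritation (a device risk named in Section 4.3) or because wearing the sensor is a burden have views that bear directly on satisfaction and empowerment. Under the plan as written they are not asked.

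Section 1.1 says that learning whether these patients will use the technology is critical before the clinics are expanded, and Aim 3c says leaders may use the answers to change operations. A result drawn mainly from those who stayed could be read as if it described everyone offered the device.

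Section 5.1 adds a reporting trap. Because finishing the survey is part of the definition of completion, a response rate calculated among completers is 100% by construction and would hide all non-response. Section 7 gives no denominator and no rule for survey non-response.

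**Working it through.** **1. Who can be surveyed, by route**

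| Route | Survey planned? | What is collected instead |
|---|---|---|
| Enrolled to six months, sensor in use | Yes (3.0, 3.3, Appendix A) | – |
| Sensor stopped, still enrolled | Yes; no section ends participation when the sensor is stopped | – |
| Withdrawn (5.2) | No | Reason, if known |
| Terminated (5.3) | No | Reason, if known (5.2 also covers investigator termination) |
| Lost to follow-up (5.4) | No | Nothing stated |

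**2. The plan's own figure.** Sections 3.2 and 7.2 enroll 125 with 20% attrition: 125 × (1 − 0.20) = 100. This reproduces. No response rate or precision is given for the survey.

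**3. CGM patients without survey data.** Assumptions, not stated in the documents: 1:1 allocation, the same attrition in both arms, and no survey from anyone counted as attrition. The CGM arm is then 125 / 2 = 62.5, so 62 or 63. At 20%, 0.20 × 62 = 12.4 and 0.20 × 63 = 12.6, so 12 to 13 are missing and about 50 can answer.

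**4. What that does to a reported proportion.** Let m be the missing share, p the proportion satisfied among responders and q the unknown proportion among the missing.

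Value for all randomized = (1 − m)p + mq

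As q runs from 0 to 1, this runs from (1 − m)p to (1 − m)p + m, a band of width m. At m = 0.20 and p = 0.90 the lower limit is 0.80 × 0.90 = 0.72 and the upper is 0.72 + 0.20 = 0.92. The values of p are illustrative; attrition of 10% and 30% shows the range.

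| Attrition m | Missing of 62–63 | p = 70% | p = 80% | p = 90% |
|---|---|---|---|---|
| 10% | 6 | 63–73% | 72–82% | 81–91% |
| 20% | 12–13 | 56–76% | 64–84% | 72–92% |
| 30% | 19 | 49–79% | 56–86% | 63–93% |

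**5. Direction.** The responder figure exceeds the all-randomized figure by p − [(1 − m)p + mq] = m(p − q). At m = 0.20 and p = 0.90:
- q = 0: 18 points too high
- q = 0.20: 14 points
- q = 0.50: 8 points
- q = 0.90: none
- q = 1: 2 points too low

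The sign depends on q, and the documents give no information about q.

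**The case against.** The case on the other side is substantial.

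- **Stopping the sensor is not leaving the study.** A reader might infer that everyone who gives up the device is left out. The documents do not support that: patients are expected to take part for six months, coordinators check in monthly (Section 4.2), and someone who stops wearing the sensor but stays enrolled gets the link. This stands, and it limits the point to patients who leave.
- **Leavers are not wholly silent.** Withdrawal reasons are recorded when known, contact can continue with specific consent, and uploaded Dexcom data also show use. This stands in part. None of it is satisfaction or behavior data, and no survey is attached to the consent exception.
- **The Section 3.0 timing is relative to each patient, and the instrument is called an exit survey.** It could be stretched to an early exit. However, Section 3.3 and Appendix A say end of study, and no exit step triggers it.
- **A definite overstatement cannot be calculated.** A reader might infer inflation of 6 to 18 points. That range arises only if 80% to 90% of responders are satisfied and at most half of the leavers are: 0.20 × (0.80 − 0.50) = 6 points and 0.20 × (0.90 − 0) = 18 points. The 20% is also all-cause attrition used to size the HbA1c analysis. Some patients without a final blood draw might still answer, and some lost patients could not be reached under any scheme. This stands.
- **Aim 3 is qualitative.** It sets no threshold or test for satisfaction, and Appendix A has a 1–5 helpfulness rating but no satisfied/not-satisfied item. This stands, and it lowers the weight of the point without removing the gap.

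**Conclusion.** The point holds in a limited form. CGM patients who withdraw, are terminated or are lost have no planned survey, so the results of Aims 3b and 3c would describe mainly those still enrolled at six months, whereas the stated target is everyone randomized to CGM.

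Under the assumptions in step 3 of the working, about one CGM patient in five would have no answers, which puts a band 20 percentage points wide around any satisfaction proportion for the randomized group. An upward bias is plausible, because patients who disliked the device may be over-represented among leavers, but the documents establish neither its direction nor its size. The HbA1c analysis is untouched. This is a minor improvement to a descriptive secondary aim of a pilot.

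**What to change.** 1. **Timing (Sections 3.0 and 3.3, Appendix A).** Offer the survey at the earlier of six months and the contact at which a patient asks to withdraw or is about to be classed as withdrawn or terminated. Keep it optional, and offer it before the no-contact rule in Section 5.2 takes effect. The monthly check-ins and resupply contacts already planned give the opportunity.
2. **Certified letter (Section 5.4).** Include the survey link.
3. **Instrument (Appendix A).** Reword items 10 and 14, which presuppose that the study was completed. Add one item on why the device was stopped; at present only open-text items could capture this.
4. **Reporting (Section 7).** Use the number randomized to CGM as the denominator for Aims 3b and 3c. Show patients enrolled to six months, early leavers and non-responders separately, with time on device. Do not use completion as defined in Section 5.1 as the base for the response rate.

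**Cost.** Wording changes, a REDCap trigger, and IRB approval of the revised letter and survey. No new visit is needed. Answers will come after different lengths of use, which is why time on device must be shown. Some leavers will still not reply, but item 4 makes that visible. The change needs to be in place before patients start to leave, because answers missed at exit are unlikely to be recovered later.

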2.0 STUDY OBJECTIVES/PURPOSE OF THE STUDY

The purpose of this study is to assess the effect of using CGM versus a standard of care (e.g. traditional fingerprick protocol) in an at-risk, diabetic patient population. The impact will be measured in terms of clinical outcomes (e.g., HbA1c level, glycemic variability), health care utilization (inpatient/outpatient visits), self-reported patient perceptions, and costs. We expect that CGM will empower patients to better manage their diabetes—ultimately, improving their health and reducing the burden of disease.

Figure 1

In this study, patients with type I and II diabetes will record their blood glucose levels since the output of the Dexcom G6 and the Contour Next ONE measure interstitial glucose. However, as noted in the *3.0 Study Design*, although the American Diabetes Association has provided a conversion table in which $\text{blood glucose} = 28.7 \times \text{A1C} - 46.7$ [6], the current standard of care is to have patients directly measure their blood glucose in the clinic rather than approximating. Thus, patients enrolled in this study will track their glucose with the general hypothesis being that those who more consistently monitor their blood glucose levels (and avoid the high peak to valley changes), will have a lower HbA1c at the end of the study. This will be tested by having HbA1c levels measured at two distinct time points: (1) at the time of enrollment, and (2) at the end of the pilot (six months). HbA1c levels may also be checked at the study midpoint (three months) if determined to be current standard of care by the provider and this data will also be considered. The aims below are written for HbA1c to confirm to the current standard of care.

Aim 1: Assess impact of CGM on glycosylated hemoglobin levels

Specific Aim 1a (primary analysis): Measure the effect of CGM vs. standard finger-prick protocol on HbA1c

- **Hypothesis for Aim 1a:** The patient-level six-month reduction in HbA1c will be greater among those randomized to CGM than that among those randomized to standard finger-prick protocol.
- **Process for Aim 1a:** We will compare the distributions of the patient-level, six-month change in HbA1c between randomized groups using the two-sided Wilcoxon rank-sum test.

Specific Aim 1b: Measure the longitudinal change in mean amplitude of glycemic excursion (MAGE) in CGM

- **Hypothesis for Aim 1b:** The patient-level daily MAGE will decrease over six months of CGM.

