3.3.1 Inclusion Criteria

- Type 1 or type 2 diabetes mellitus with a HbA1c $\geq 6.5\%$
- Patients that are currently managing their glucose levels for diabetes with a glucose meter (or will be prescribed one by their healthcare provider)
- Patients that are treated within the four Reimagine Primary Care clinics (Cottonwood Family Medicine, Cottonwood Senior, Avenues Internal Medicine, and Holladay Internal Medicine).
- Patients 18-80 years of age

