7.1 Statistical Considerations

The primary analysis (Aim 1a) will measure the intervention effect on the patient-level six-month absolute reduction in mean HbA1c. Since not all patients will have their final HbA1c test at six months exactly, we will estimate each patient's six-month reduction in HbA1c by interpolating/extrapolating from their assessments, given that their HbA1c levels were assessed on at least two occasions: baseline, and >3 months post baseline. Then, among patients with a sufficient number of occasions of HbA1c assessments, we will estimate their sixmonth HbA1c using generalized linear mixed models with patient-level random slopes and intercepts, with appropriate link function and distributional family [8]. The quantitative secondary analyses (Aims 1b-e, 2a-b) will use outcomes related to the longitudinal change in various metrics of glycemic variability (MAGE, C_v , range) as well as the frequency of hypoglycemic events, healthcare utilization, and cost. The secondary analyses will also use longitudinal data analysis to assess whether there is a significant reduction in glycemic variability over six months (Aims 1b-d) among those randomized to CGM, whether there is a significant reduction in hypoglycemic events over six months (Aim 1e) among those randomized to CGM, and to assess whether overall healthcare utilization and costs differ between randomized groups [9]. Accordingly, specific aims 1b-e will rely heavily on longitudinal data analysis within a multilevel/hierarchical framework [10], specifically using generalized linear mixed models. In the sensitivity analyses, provider variability will be accounted for using three-level (provider, patient, occasion), quasi-Bayesian generalized linear mixed models [11]. Finally, the sensitivity analyses exploring HTE will use generalized additive models (GAM) to identify subgroups of patients for whom CGM is likely to have a differential effect [12-13].

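### Diabetes type is controlled neither in the allocation as described nor in the primary rank-sum test, so a chance imbalance in type between arms would go uncorrected

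*Combined protocol and SAP*

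**What the plan says.** Section 3.0 presents a "parallel randomized controlled trial of CGM versus a standard finger-prick protocol among patients with type I and II diabetes", and the first inclusion criterion in Section 3.3.1 opens with "Type 1 or type 2 diabetes mellitus with a HbA1c". Both types therefore enter one comparison.

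On allocation, Section 3.0 says only that "patients will be randomized into one of two groups", that the list is made in advance "using a random number generator from Microsoft Excel", that the numbers go into concealed envelopes, and that the coordinator will "hand the patient the earliest numbered envelope to randomize". No section mentions blocks, strata, minimisation, an allocation ratio, target arm sizes or a separate envelope series for any group of patients.

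On analysis, Aim 1a (Section 2.0) compares six-month HbA1c change "between randomized groups using the two-sided Wilcoxon rank-sum test". Section 7.1 estimates each patient's six-month value with a mixed model and names no term for diabetes type. It adds that "the sensitivity analyses exploring HTE will use generalized additive models (GAM) to identify subgroups of patients". Section 7.0 labels that work exploratory, and neither section names diabetes type. No section gives the expected split between types.

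**The concern.** Diabetes type is an eligibility item, so it is known before the envelope is opened. It is also a plausible predictor of how far HbA1c moves over six months. A plan that mixes the types on purpose would usually control type when allocating, when analysing, or both. Here nothing described does either.

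Randomization keeps the comparison unbiased on average over repeated trials. In this single trial, the rarer type could by chance fall mostly into one arm. If the types differ in mean change, part of the observed difference between arms would then reflect type rather than CGM. A plain rank-sum test has no means of separating the two. The stake is the credibility and precision of the primary contrast, not the validity of the p-value.

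**Working it through.** **Inputs from the documents.** 125 enrolled, 20% attrition, 100 analysed; illustrative difference of 1 HbA1c point with SD of change 1.25 (Section 7.2); two-sided rank-sum test (Aim 1a).

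**Assumed, because not stated.** 1:1 allocation; alpha 0.05; rarer-type share of 5% to 30%; difference between types in mean HbA1c change of 0.5 to 1.0 points.

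**Step 1: the plan's own figure.** 125 × (1 − 0.20) = 100, and d = 1/1.25 = 0.8. With 50 per arm, power = Φ(0.8/√(2/50) − 1.96) = Φ(2.04) = 97.9%, or 97.4% with the rank-sum efficiency factor 3/π. The claim of more than 80% at d = 0.8 holds with room to spare.

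**Step 2: total arm sizes.** Under simple 1:1 randomization of 125, P(70:55 or worse) = 0.21 (binomial). The cost is trivial: the SE rises by the factor √[(1/55 + 1/70)/(2/62.5)] = 1.007. Even 60:40 among 100 analysed lowers t-test power only from 97.7% to 97.3% at d = 0.8, and from 80.6% to 79.0% at d = 0.57.

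**Step 3: split of the rarer type.** With m patients of that type, the number in one arm is Binomial(m, 0.5). The last column assumes instead a list fixed at 62/63 overall but unstratified (hypergeometric).

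| Assumed share | m | 2:1 or worse | 3:1 or worse | 2:1 or worse, fixed 62/63 |
|---|---|---|---|---|
| 5% | 6 | 0.69 | 0.22 | 0.68 |
| 10% | 12 | 0.39 | 0.15 | 0.36 |
| 20% | 25 | 0.11 | 0.015 | 0.07 |
| 30% | 38 | 0.03 | 0.002 | 0.01 |

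**Step 4: effect on the primary contrast.** Shift = (m₁/62 − m₂/63) × difference in mean change between types. This takes attrition to be unrelated to type.

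| Split | Difference in share | Shift (0.5 to 1.0 points) |
|---|---|---|
| 8:4 of 12 | 0.129 − 0.063 = 0.066 | 0.03 to 0.07 |
| 9:3 of 12 | 0.145 − 0.048 = 0.098 | 0.05 to 0.10 |
| 17:8 of 25 | 0.274 − 0.127 = 0.147 | 0.07 to 0.15 |

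The SE of the contrast is 1.25 × √(2/50) = 0.25, so a shift of 0.05 to 0.15 is 0.2 to 0.6 of one SE. Section 1.1 cites telehealth effects of about 0.50 to 0.55 points; against 0.50, the shift is 10% to 30%.

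**Step 5: power and type I error.** Simulation, 100 analysed, normal outcomes, 3,000 runs per scenario. A type difference of 0.8 SD equals 1.0 HbA1c point at SD 1.25.

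| d | Share | Type difference (SD) | Plain list, plain test | Plain list, van Elteren | Stratified list, van Elteren |
|---|---|---|---|---|---|
| 0.57 | 10% | 0 | 77.9% | 77.5% | 78.1% |
| 0.57 | 10% | 0.8 | 76.0% | 77.9% | 78.2% |
| 0.57 | 20% | 0.8 | 74.4% | 77.8% | 78.2% |
| 0.8 | 10% | 0 | 96.6% | 96.2% | 96.8% |
| 0.8 | 10% | 0.8 | 96.2% | 96.8% | 97.4% |
| 0.8 | 20% | 0.8 | 95.2% | 96.8% | 97.4% |

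Monte Carlo SE near 77% is √(0.77 × 0.23/3000), about 0.8 points. A further set of runs, with shares of 5% to 20% and type differences of 0 to 0.8 SD, gave about −1 to +3 points for the change of test alone. At d = 0.57, the stratified list with the plain test gives 75.0% (20% share) and 77.0% (10% share), so most of the gain comes from the stratified test. Simulated type I error was between 4.2% and 5.5% throughout.

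**The case against.** The strongest reply is that simple randomization of 125 patients in a pilot is a legitimate choice, that the test keeps its error rate, and that the gain is small and rests on stacked assumptions. Most of that stands. The share and the type difference are both assumed, and the SD of 1.25 is only a worked example in Section 7.2. At a 30% share, a bad split is unlikely.

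Four stronger readings are tempting, and the documents do not support them:

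- A reader might infer that the list is an unrestricted coin-flip sequence. Section 3.0 is silent, and an Excel shuffle of a fixed 62/63 list would fit its words equally well. The type imbalance hardly depends on this, as the last column of Step 3 shows.
- A reader might infer that type 1 patients will be few. No section gives a split or says which type is rarer.
- A reader might infer that lopsided arm sizes threaten the trial. Step 2 shows that they do not.
- A reader might infer that a planned subgroup analysis by type is at risk. The heterogeneity analyses are exploratory and do not name type. Balance would not rescue them either: with 12 patients split 6:6, the SE of the effect is 1.25 × √(1/6 + 1/6) = 0.72, against 0.83 at 9:3. Both are uninformative, because the limit is the number of patients.

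It is also fair to say that blocks in a small stratum make some allocations easier to guess when the device given is visible to patient and coordinator. Varying, concealed block sizes reduce this without removing it.

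What the reply does not answer is that a chance imbalance in type, if it occurs, cannot be corrected by the planned primary test, and that the remedy costs almost nothing.

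**Conclusion.** The point holds as a modest, worthwhile improvement. As written, the plan controls diabetes type neither at allocation nor in the primary test. The chance of a 2:1 or worse split of the rarer type runs from about 0.69 at a 5% share to 0.03 at 30%. For the 9:3 and 17:8 splits worked above, the uncorrected shift is about 0.05 to 0.15 HbA1c points if the types differ by 0.5 to 1.0 points in mean change. Share and type difference are assumptions, and the conclusion weakens if type is unrelated to HbA1c change or if the rarer type is common. Type I error is not at issue, total arm size is not a material harm, and the power change is about −1 to +4 points. The case rests on protection against an imbalance that could not otherwise be corrected, more than on power.

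**What to change.** In Section 3.0, state 1:1 allocation in permuted blocks of varying, concealed size, generated separately for type 1 and type 2, with one numbered envelope series per type. In Aim 1a and Section 7.1, pre-specify the rank-sum test stratified by diabetes type (van Elteren), or an analysis adjusted for type.

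If enrollment has started, leave the allocation alone. Make only the analysis change, before outcomes are examined, and report diabetes type by arm.

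The cost is a new list, a second envelope series and one line in the analysis section, with no extra patients or procedures. The downsides are slightly more envelope handling, slightly greater predictability of the blocks, and a negligible loss of power if type turns out to be unrelated to HbA1c change.
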